### 8.1 Administrative and General Procedures

### **8.1.1** Informed Consent

The investigator or medically qualified designee (consistent with local requirements) must obtain documented informed consent from each potential participant (or their legally acceptable representative) prior to participating in this clinical study or FBR. If there are changes to the participant's status during the study (eg, health or age of majority requirements), the investigator or medically qualified designee must ensure the appropriate documented informed consent is in place.

29-JUN-2022

PRODUCT: MK-1088

PROTOCOL/AMENDMENT NO.: 002-01

## 8.1.1.1 General Informed Consent

Informed consent given by the participant or their legally acceptable representative must be documented on a consent form. The form must include the study protocol number, study protocol title, dated signature, and agreement of the participant (or their legally acceptable representative) and of the person conducting the consent discussion.

A copy of the signed and dated informed consent form should be given to the participant (or their legally acceptable representative) before participation in the study.

The initial ICF, any subsequent revised ICF, and any written information provided to the participant must receive the IRB/IEC's approval/favorable opinion in advance of use. The participant or their legally acceptable representative should be informed in a timely manner if new information becomes available that may be relevant to the participant's willingness to continue participation in the study. The communication of this information will be provided and documented via a revised consent form or addendum to the original consent form that captures the participant's or the participant's legally acceptable representative's dated signature.

If the investigator recommends continuation of study intervention beyond disease progression, the participant or their legally acceptable representative will be asked to provide documented informed consent.

Specifics about the study and the study population are to be included in the study informed consent form.

Informed consent will adhere to IRB/IEC requirements, applicable laws and regulations, and Sponsor requirements.

## 8.1.1.2 Consent and Collection of Specimens for Future Biomedical Research

The investigator or medically qualified designee will explain the FBR consent to the participant, or the participant's legally acceptable representative, answer all of their questions, and obtain documented informed consent before performing any procedure related to FBR. A copy of the informed consent will be given to the participant before performing any procedure related to FBR.

### 8.1.2 Inclusion/Exclusion Criteria

All inclusion and exclusion criteria will be reviewed by the investigator, who is a qualified physician, to ensure that the participant qualifies for the study.

# 8.1.3 Participant Identification Card

All participants will be given a participant identification card identifying them as participants in a research study. The card will contain study-site contact information (including direct telephone numbers) to be used in the event of an emergency. The investigator or qualified designee will provide the participant with a participant identification card immediately after

PROTOCOL/AMENDMENT NO.: 002-01

the participant provides documented informed consent. At the time of intervention allocation, site personnel will add the treatment/randomization number to the participant identification card.

The participant ID card also contains contact information for the emergency unblinding call center so that a health care provider can obtain information about study intervention in emergency situations where the investigator is not available.

# **8.1.4 Medical History**

A medical history will be obtained by the investigator or qualified designee. Medical history will include all active conditions, and any condition diagnosed within the prior 10 years that are considered to be clinically important. Details regarding the disease for which the participant has enrolled in the study will be recorded separately and not listed as medical history.

If a medical condition is diagnosed at the time of screening due to the physical examination, laboratory tests, radiologic assessment, other assessment, and/or a combination of these evaluations, the medical condition is to be recorded as a baseline condition along with the participant's other medical history unless due to any protocol-specified intervention (eg, procedure, washout or run-in treatment including placebo run-in).

## 8.1.5 Prior and Concomitant Medications Review

#### **8.1.5.1** Prior Medications

The investigator or qualified designee will review prior medication use, including any protocol-specified washout requirement, and record prior medication taken by the participant within 28 days before first dose of study intervention.

## **8.1.5.2** Concomitant Medications

The investigator or qualified designee will record medication, if any, taken by the participant during the study.

All medications related to reportable SAEs and ECIs should be recorded as defined in Section 8.4.

All new anticancer therapy initiated after the study start must be recorded in the eCRF. If a participant initiates another anticancer therapy other than the assigned study intervention(s), the study intervention(s) should be discontinued and the participant will move into the Survival Follow-up Phase; if a participant initiates a new anticancer therapy within 30 days after the last dose of the study intervention, the 30-day Safety Follow-up Visit should occur before the first dose of the new therapy.

## 8.1.6 Assignment of Screening Number

All consented participants will be given a unique screening number that will be used to identify the participant for all procedures that occur before intervention allocation. Each participant will be assigned only 1 screening number. Screening numbers must not be reused for different participants.

# 8.1.7 Assignment of Treatment/Randomization Number

All eligible participants will be allocated, by nonrandom assignment, and will receive a treatment/randomization number. The treatment/randomization number identifies the participant for all procedures occurring after treatment allocation. The assigned screening number will become the participants' treatment/randomization number. Once a treatment/randomization number is assigned to a participant, it can never be reassigned to another participant.

A single participant cannot be assigned more than 1 treatment/randomization number.

# 8.1.8 Study Intervention Administration

Study intervention should begin within 3 days of treatment allocation.

## **8.1.8.1** Timing of Dose Administration

For infusion:

Study intervention(s) will be administered by the investigator and/or study staff according to the specifications within the Pharmacy Manual. The total volume of study intervention infused will be compared with the total volume prepared to determine compliance with each dose administered.

## Oral medication:

During on-site visits, study intervention(s) will be administered by the investigator and/or study staff according to the specifications within the Pharmacy Manual. The administration, the dose, the time of administration, as well as any immediate reactions at the time of intake will be documented in the eCRF.

For nonvisit days, MK-1088 will be taken at home. The participant will note the number of tablets taken, the time of administration, as well as any reactions including the date/time.

When a participant attends a study visit, they will bring any unused tablets.

## 8.1.8.2 Timing of Administration for MK-1088

MK-1088 is a tablet administered orally once a day from Day 1 to Day 21 of each treatment cycle. The reason for any variability in administration of MK-1088 outside the protocol-

specified window should be documented in the participant's medical chart and recorded on the eCRFs.

Every effort should be made to begin the first dose of study intervention on the day of allocation, but if this is not achieved, study intervention should be initiated no later than 3 days from the date of allocation. All subsequent cycles of study intervention may be administered up to 3 days before or 3 days after the scheduled Day 1 of each cycle due to administrative reasons per the investigator's judgment. All study interventions will begin on Day 1 of each cycle after all predose study procedures and assessments have been completed as detailed in Section 1.3.

The Pharmacy Manual contains specific instructions for MK-1088 dose calculation and administration.

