Part 1 Arm 1 and Arm 2: MK-1088 Administration/Dispense		X				X				X			X		MK-1088: taken orally QD from D1 through D21 of each treatment cycle.
Part 1 Arm 2: Pembrolizumab Administration		X				X				X			X		Pembrolizumab: administered IV Q3W on D1 of each treatment cycle.
Anticancer Therapy Status														X	Any changes in new treatment will be collected.
Disease Status														X	
Clinical Procedures/Assessme	nts														
Full Physical Examination	X													X	
Directed Physical Examination		X		X	X	X				X			X		
Height	X														
Weight	X	X				X				X				X	
Vital Signs	X	X	X	X	X	X	X	X	X	X	X	X	X	X	Obtain heart rate, respiratory rate, blood pressure, temperature.
12-lead Electrocardiogram	X	X	X			X	X								C1D1 and C2D1: Obtain predose and 2 hrs postdose. C1D2 and C2D2: Obtain predose.

Study Phase	Screening Phase a	Treatment Phase (3-Week Cycles)											End of Treatment	Notes	
Treatment Cycle/Title:	Screening (Visit 1)		Сус	le 1			Су	cle 2		(	Cycle :	3	Cycles 4 to 35	/Discon- tinuation	Notes
Treatment Days per Cycle:	Up to 28 days before Day 1 Cycle 1	Day 1 b	Day 2°	Day 8	Day 15	Day 1	Day 2°	Day 8	Day 15	Day 1	Day 8	Day 15	Day 1	At time of treatment discontinuation	Treatment Phase: Procedures, assessments, and samples are collected predose unless otherwise specified .
Scheduling Window (Days)	-28 to -1	0	0	±3	±3	±3	±3	±3	±3	±3	±3	±3	±3	+3	
ECOG Performance Status	X	X	x									X	Obtain within 72 hrs before the first dose of study intervention on D1 of each cycle.		
AE Monitoring	X	+											→	X	
Tumor Imaging Response Assessment (PCWG-modified RECIST 1.1 for prostate cancer participants; RECIST 1.1 for all other participants)	X	4 -	4										X	Treatment phase schedule:  Obtain every 9 weeks (±7 days)  After 54 weeks, obtain every 12 weeks (±7 days)	
Prostate cancer participants only: Bone Scan	X	4						·				Х	Tc99 bone scintigraphy (nuclear medicine bone scan) is required at screening and on-study at all protocol-required tumor assessment visits and when clinically indicated.  Tumor assessments visits:  Obtain every 9 weeks (±7 days)  After 54 weeks, obtain every 12 weeks (±7 days)		

Study Phase	Screening Phase a		Treatment Phase (3-Week Cycles)									End of Treatment	Notes		
Treatment Cycle/Title:	Screening (Visit 1)		Cycle 1 Cycle 2 Cycle 3 Cycles 4 to 35								/Discon- tinuation	Notes			

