Plasma for MK-1088 PK assay		X	X			X	X			X			X	X	On the day(s) of sample collection, participants must not take study medication until the predose PK and biomarker (Section 8.8) sample collections are complete. Document the time of the last MK-1088 dose (ie, at home) taken before PK collection.  C1D1 and C2D1: Obtain predose and 1, 2, 4, and 8 hrs postdose.  C1D2 and C2D2: Obtain predose (24 hrs after D1 dosing for C1 and C2)  C3, C4 and every 4 cycles (ie, C4, C8, etc): Obtain predose
Blood for Serum Biomarker Analysis		X				X				X					Obtain predose
Blood for RNA Analyses		X				X				X					Obtain predose
Tumor Tissue Collection															
Archival or Newly Obtained Tumor Tissue Collection	X														See detailed tissue collection requirements in the Procedure/Lab Manual.  Participants in Arm 1 who cross over to Arm 2 do not need to provide an additional sample.

PROTOCOL/AMENDMENT NO.: 002-01

AE=adverse event; aPTT= activated partial thromboplastin time; β-hCG=beta-human chorionic gonadotropin; C=Cycle; CR=complete response; CT=computed tomography; D=Day; ECOG=Eastern Cooperative Oncology Group; HIV= human immunodeficiency virus; MRI=magnetic resonance imaging; PCWG=Prostate Cancer Working Group; PET= positron emission tomography; PK=pharmacokinetic; PSA=prostate-specific antigen; PT/INR=prothrombin time/international normalized ratio; PTT= partial thromboplastin time; Q3W=every 3 weeks; QD=once daily; RECIST=Response Evaluation Criteria In Solid Tumors; RNA=ribonucleic acid; SOP=standard operating procedure; TSH=thyroid-stimulating hormone; WOCBP=women of childbearing potential.

- a Arm 1 crossover to Arm 2: Screening assessments obtained during Arm 1 may be eligible for crossover screening for Arm 2 if the assessments were obtained within 28 days before Arm 2 treatment initiation.
- b Laboratory tests should be performed within 3 days before the first dose of study intervention. An exception is hepatitis and thyroid serologies, which may be performed within 28 days before the first dose. Please refer to Section 8.3.4.1 for details.
- c C1D2 and C2D2 evaluations must be obtained within 24 hours after study intervention administration for C1D1 and C2D1.

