#### 2.2.3.1 MK-1088 Clinical Studies

The FIH study for MK-1088 was PN001, a single ascending dose study in healthy volunteers to assess the safety, tolerability, and PK of MK-1088. This study completed enrollment and achieved LPLV on 01-JUN-2021. The FIH study in healthy volunteers afforded the advantage of rapid dose escalation into the therapeutic dose range in the subsequent Phase 1/Phase 2 study in oncology patients while also offering more comprehensive and reliable measurement of MK-1088 plasma exposures to thoroughly characterize the PK of MK-1088. Single doses of 1, 3, 10, 25, 50, 100, 150, and 224 mg of MK-1088 were evaluated in PN001. Doses up to 224 mg were generally well tolerated, with no major AEs and SAEs observed at the dose range of 1 to 224 mg. Increases in blood pressure of up to 14 mm Hg along with increases in heart rate of up to approximately 2 to 13 bpm were observed over the dose range of 10 to 224 mg. One participant at the highest dose of 224 mg had a greater systolic blood pressure/heart rate response than others (3× mean) and diastolic blood pressure increase similar to mean but did not report any associated symptoms.

Plasma exposures in PN001 were generally dose proportional at the 1 to 224 mg dose range, with observed median  $T_{max}$  of 2 hours and apparent terminal  $t_{1/2}$  between 6 to 11 hours. The minimum  $C_{trough}$  concentration target of 0.3  $\mu$ M corresponding to >99% TE for  $A_{2A}$  and >80% for  $A_{2B}$  was successfully achieved at a single dose of 150 mg while the aspirational trough target of 1  $\mu$ M corresponding to >99% for  $A_{2A}$  and >90% for  $A_{2B}$  was attained at both the 12- and 24-hour time points at a dose of 224 mg of MK-1088, enabling QD dosing of MK-1088 in Phase 1b. Furthermore, no food effect was observed at the 50 mg dose. Data from this FIH study were applied to inform the starting dose and dose levels for PN002 based on overall safety, tolerability profile, and PK of MK-1088 from PN001.

Please refer to the IB for further details.

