Throughout the study, the first intake of MK-1088 will occur at the trial site on Day 1 of each cycle for Arm 1 and Arm 2 (shortly before the pembrolizumab infusion in Arm 2). MK-1088 will be administered orally, once daily. While in the clinic setting, pembrolizumab will be administered through an IV infusion as described in the Pharmacy Manual. Subsequent dosing of MK-1088 will be administered once daily QD by the participant (ie, unsupervised at their home) at approximately the same time each day, until Day 1 of the next cycle. For the MK-1088 dose on Day 2 of Cycles 1 and 2, the participant should refrain from MK-1088 administration until required study procedures on this day (eg, blood draw for MK-1088 PK assay) have been completed.

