# 9.6.3.2 Pharmacokinetic and Pharmacodynamic Modeling Analysis

PK parameters of study interventions will be summarized by planned visit and time for each dose separately.

PK and pharmacodynamics modeling analyses will be documented in the sSAP.

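### Dosing instructions conflict for the days between Day 21 and a late Day 1, and predose PK samples taken after a gap can be pooled with true 24-hour troughs

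*Combined protocol and SAP*

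**What the plan says.** Three places limit daily MK-1088 to 21 days per cycle. The note in Table 1 (Section 1.3.1.1) reads "MK-1088: taken orally QD from D1 through D21 of each treatment cycle", Table 5 gives the same days, and Section 8.1.8.2 states "MK-1088 is a tablet administered orally once a day from Day 1 to Day 21 of each treatment cycle". The text of Section 6.1 says participants dose at home "at approximately the same time each day, until Day 1 of the next cycle". Section 8.1.8.2 adds that cycles after the first "may be administered up to 3 days before or 3 days after the scheduled Day 1 of each cycle", for administrative reasons. Outside the text of Section 6.1, nothing says what a participant does between Day 21 and a late Day 1.

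Table 1 specifies "C1D1 and C2D1: Obtain predose and 1, 2, 4, and 8 hrs postdose", a further predose sample on Day 2 of Cycles 1 and 2 (24 h after the Day 1 dose), and predose samples at Cycles 3, 4, 8 and so on. Table 1 and Section 8.6 also call for the time of the last dose before collection to be documented.

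Section 9.6.3.2 says "PK parameters of study interventions will be summarized by planned visit and time for each dose separately". Sections 8.6 and 9.1 likewise use planned visits and times, and Section 9.1 lists Cmin among the secondary PK parameters.

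**The concern.** When Day 1 is late, a site following the 21-day rule leaves 1 to 3 days without drug, and a site following Section 6.1 leaves none. Both comply with some part of the protocol. The gap falls immediately before the Day 1 samples, and the half-life is short, so predose values from the two kinds of site measure different things under the same visit label.

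This matters because PN001 was a single-dose study, so Cycle 2 here gives the only serial profile after repeat dosing. Section 2.2.3.1 states the exposure target as a trough (0.3 µM minimum, 1 µM aspirational) and uses the 24-h level to support once-daily dosing. PK also feeds decisions: possible BID dosing (Section 4.1), whether exposure keeps rising with dose (Section 4.3.1.1), and changes to the escalation schedule (Section 4.3.1.3). A trough that is low because of the visit date could be read as a property of the drug.

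**Working it through.** The plan gives no figure of its own on this point, so there is none to reproduce.

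**Inputs**
- Terminal half-life t½ "between 6 to 11 hours" and median Tmax 2 h (Section 2.2.3.1, single dose, healthy volunteers).
- Dosing interval 24 h.
- Delay d = 0 to 3 days (Section 8.1.8.2).
- Assumptions: linear kinetics at every dose level, and the healthy-volunteer half-life holds in patients.

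**Step 1. Fraction left after one dosing interval.** r = 2^(−24/t½).
- t½ = 6 h: r = 2^(−4) = 0.0625.
- t½ = 11 h: r = 2^(−24/11) = 0.2204.

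**Step 2. Day 1 predose level relative to the steady-state trough, dosing stopped at Day 21.** The last dose is 24(d+1) h earlier, so the ratio is r^d.

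| Delay | Hours since last dose | t½ 6 h | t½ 11 h |
|---|---|---|---|
| 0 (or early start) | 24 | 100% | 100% |
| 1 day | 48 | 6.3% | 22.0% |
| 2 days | 72 | 0.4% | 4.9% |
| 3 days | 96 | 0.02% | 1.1% |

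As an illustration, a true trough of 1.0 µM would read 0.06 to 0.22 µM after a one-day delay, below the 0.3 µM minimum target. If dosing continues until the next Day 1, the ratio is 100% for any start within the window.

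**Step 3. Cycle 2 Day 2 sample, 24 h after the Day 1 dose.** Relative to steady state it is (1 − r) + r·r^d.
- t½ = 6 h, d = 1: 0.9375 + 0.0625 × 0.0625 = 0.941. At d = 3 it is 0.938.
- t½ = 11 h, d = 1: 0.7796 + 0.2204 × 0.2204 = 0.828. At d = 3 it is 0.782.

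**Step 4. Cycle 2 Day 1 profile.** A one-compartment oral model with absorption set to give Tmax = 2 h, for d = 1 to 3, relative to steady state:

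| Quantity | t½ 6 h | t½ 11 h |
|---|---|---|
| Cmax | 93-94% | 77-82% |
| AUC0-8 | 93% | 77-81% |
| AUC0-24 | 93-94% | 77-82% |

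**Step 5. Comparison with accumulation.** The accumulation ratio is 1/(1 − r): 1.07 at 6 h and 1.28 at 11 h. Losing all of it means a fall of 1 − 1/1.067 = 6% or 1 − 1/1.283 = 22%. The shortfalls in Steps 3 and 4 run from about 6% to 23%. The apparent ratio of the Cycle 2 to the Cycle 1 Day 2 sample is the product of accumulation and Step 3. At t½ = 11 h it is 1.283 × 0.828 = 1.06 after one missed day and 1.283 × 0.782 = 1.00 after three, against a true 1.28.

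**Step 6. Effect on a pooled trough.** If a share p of predose values follows a one-day gap and the others are true troughs, the pooled mean is 1 − p(1 − r) of the true value. The documents do not give p. It can lie anywhere from 0 to 1, so the mean lies between 100% and 6-22% of the true trough.

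**The case against.** A reader might infer that all repeat-dose PK in the trial becomes uninterpretable. The documents do not support that. The two rules coincide whenever Day 1 is on time or early. They differ only for a late Day 1 at a site that stops at Day 21, and the number of such cycles could be zero. The Cycle 2 Day 2 sample is a true 24-h level after an on-site dose, so the trough targets can still be assessed approximately in Cycle 2. With accumulation this small, Cmax and AUC change modestly. All of this stands and limits the point.

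It can also be said that Section 4.1 describes dosing on every day of a 21-day cycle, that Day 1 to Day 21 merely names those days without ordering a break, and that Section 6.1 is the only text addressing the interval. That is a possible reading, but Tables 1 and 5 and Section 8.1.8.2 do not say it, and a site working from Table 1 would not find it. The Pharmacy Manual may settle the matter but is not part of these documents.

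Finally, the data needed to identify affected samples are collected: last-dose time, home-dose times (Section 8.1.8.1) and tablet counts (Section 6.4). Section 9.5.2 lets values be excluded with reasons, and PK modelling is left to the sSAP. So it is not certain that affected values will be averaged in. But Section 9.5.2 turns on compliance and major violations, and a participant who stopped at Day 21 and returned within the window complied with three parts of the protocol. No stated rule uses time since last dose for the secondary-endpoint summaries.

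**Conclusion.** The point holds in a limited form. The current text conflicts on MK-1088 dosing for up to 3 days before a late Day 1. Where dosing stops at Day 21, the predose sample drops to at most 22% of the steady-state trough, and the stated summaries would allow it to be pooled with 24-h troughs. The Cycle 2 post-dose samples and Day 2 level lose only about 6-23%. That is small for describing exposure, but it removes most or all of the accumulation that the Cycle 2 profile could show.

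The percentages rest on linear kinetics and on a single-dose, healthy-volunteer half-life carried over to patients at every dose level. How many samples are affected cannot be worked out from the documents. The primary DLT endpoint is not part of this point.

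**What to change.** 1. Reconcile Table 1, Table 5 and Section 8.1.8.2 with the text of Section 6.1, so that one statement covers the days between Day 21 and a late Day 1. Which rule applies is for the sponsor to decide.

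2. In Sections 8.6 and 9.6.3.2, state that a Day 1 predose sample from Cycle 2 onward is summarised as Cmin, and a Cycle 2 Day 1 profile as steady state, only if the recorded last dose was about 24 h earlier and no doses were missed on the immediately preceding days. The sponsor should prespecify the tolerance around 24 h; the documents give no basis for a particular width. Flag all other samples and analyse them by actual time since last dose.

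The cost is a wording correction and a short addition to the PK sections. No new samples or data items are needed. Somewhat fewer values will count as steady state; how many depends on the unknown share of late cycles.
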